8.2 Toxicity Criteria

Toxicities and adverse events will be recorded and categorized according to severity, relationship to procedure, and relationship to the study procedure or study drugs. Level of toxicity is based on the NCI CTCAE criteria.

8.3 Pregnancy

If, following initiation of the investigational product, it is subsequently discovered that a study participant is pregnant or may have been pregnant at the time of investigational product exposure, including during at least 5 half-lives after product administration, the investigational product will be permanently discontinued in an appropriate manner (eg, dose tapering if necessary for participant). The patient will continue to be followed until the outcome of the pregnancy can be determined, and will then continue with routine surveillance imaging as per the protocol.

8.4 Overdose

An overdose is defined as the accidental or intentional administration of any dose of a product that is considered both excessive and medically important. All occurrences of overdose must be reported as an SAE.

8.5 Other Safety Considerations

Any significant worsening noted during interim or final physical examinations, electrocardiograms, x-rays, and any other potential safety assessments, whether or not these procedures are required by the protocol, should also be recorded as a nonserious or serious AE, as appropriate, and reported accordingly.

8.6 Criteria for Individual Subject Withdrawal from the Study

Subjects may withdraw from the study at any time for the following reasons:

1. Subject's prerogative: The subject desires to discontinue participation in this study.

2. Investigator's prerogative: The subject is unwilling or unable to comply with the protocol.

Subjects must discontinue study drugs for the following reasons:

- 1. The biopsy indicates that the patient does not have a true pathological recurrence of their tumor
- 2. The patient experiences a grade 3 or 4 toxicity during Phase 1 of the trial which precludes the completion of the inpatient monitoring period
- 3. The patient experiences a toxicity consistent with the Nivolumab prescribing information that requires discontinuation of Nivolumab. Such toxicities will be deemed sufficient to discontinue both Nivolumab and BMS-986016. Specifically, these toxicities are:
 - a. Immune-mediated pneumonitis: Grade 3 or 4 immune-mediated pneumonitis will prompt automatic discontinuation of study drugs
 - b. Immune-mediated colitis: Grade 4 immune-mediated colitis will prompt automatic discontinuation of study drugs
 - c. Immune-mediated hepatitis: Grade 3 or 4 immune-mediated hepatitis will prompt automatic discontinuation of study drugs
 - d. Immune-mediated endocrinopathies: Grade 4 immune-mediated hypophysitis; Grade 3 or 4 immune-mediated adrenal insufficiency; and Grade 4 hyperglycemia will prompt automatic discontinuation of study drugs. Additionally, thyroid function will be followed, and thyroid hormone replacement will be given as needed
 - e. Immune-mediated nephritis and renal dysfunction: Grade 4 serum creatinine elevation will prompt automatic discontinuation of study drugs
 - f. Immune-mediated skin adverse reactions: Grade 4 rash will prompt automatic discontinuation of study drugs
 - g. Immune-mediated encephalitis: Grade 4 encephalitis will prompt automatic discontinuation of study drugs
 - h. Infusion reactions: Grade 3 or 4 infusion reactions will prompt automatic discontinuation of study drugs
 - i. In addition to the above, due to the report of myocarditis in one patient on the combination of BMS-986016 and Nivolumab, Grade 4 myocarditis will prompt automatic discontinuation of study drugs
- 4. Clinical progression
- 5. Confirmed radiological progression and investigator determination that the patient is no longer benefiting from treatment with the study treatment

If study drug is discontinued, the patient will enter the survival follow-up phase of the study.

Additionally, if a patient is removed from the study for clinical or radiological progression of disease, we will perform a follow-up assessment at the next scheduled imaging visit and no less than 4 weeks after the prior assessment of disease progression.

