Administer the infusion over 30 minutes through an intravenous line containing a sterile, non-pyrogenic, low protein binding in-line filter (pore size of 0.2 micrometer to 1.2 micrometer). Do not coadminister other drugs through the same intravenous line. Flush the intravenous line at end of infusion with appropriate amount of diluent (e.g. 15-20 ml) to ensure that the total dose is administered. Total infusion and flush time should equal to 30 minutes.

Nivolumab should not be infused concomitantly in the same intravenous line with other agents. No physical or biochemical compatibility studies have been conducted to evaluate the co-administration of Nivolumab with other agents.

First Nivolumab dose infusion monitoring

Monitoring for an infusion reaction and cytokine release on day 3 of the protocol will consist of clinical observation with q15 minute vital signs, including temperature, during and for the first hour after infusion. Specifically, we will be checking the patients for fever, chills, shakes, itching, rash, hypertension or hypotension or difficulty breathing during the administration or immediately afterwards (within the following 2 hours). The patients will be treated according to I-O AE Algorithms from Appendices B and C; Investigator Brochures for Nivolumab (BMS-936558) and Relatlimab (BMS-986016). Generally, Grade 1 infusion reactions will be observed. Grade 2 or 3 infusion reactions will prompt interruption of the patient's infusion until the observed symptom returns to the level of a Grade 1 reaction. Patients will be given 25mg of Benadryl IV and 650 mg of Tylenol PO for any grade 2 or 3 reaction. The Benadryl can be repeated once for symptom resolution until the reaction returns to a level of Grade 1. If a patient has a Grade 2 or 3 reaction, subsequent infusions will be preceded by 25mg of Benadryl IV and 650mg of Tylenol PO 30 minutes prior to dosing. Grade 4 reactions will cause discontinuation of the therapy. Please see section 1.6.5 for monitoring of combined infusions, below.

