1.6.7 Infusion monitoring for combination of Nivolumab and BMS-986016

Monitoring for an infusion reaction and cytokine release on Day 17 (+/-2 days) of the protocol will consist of clinical observation in the day hospital ward or 7SW of the NIH Clinical Center. The total infusion monitoring time will be expected to last 4-5 hours for most patients. First, the patient will receive Nivolumab as an IV infusion over 30 minutes. Patients with a prior Grade 2 or 3 infusion reaction will have pretreatment with 25mg of Benadryl IV together with 650mg of Tylenol PO. During both infusions, patients will have q15 minute vital signs, including temperature, pulse, blood pressure and pulse oximetry. BMS-986016 infusion will begin 15-30 minutes after completion of the Nivolumab infusion. BMS-986016 will then be given as an IV infusion over 60 minutes with ongoing monitoring. The patients will also be monitored for two hours after completion of the BMS-986016 in the day hospital or 7SW. Specifically, we will be checking the patients for fever, chills, shakes, itching, rash, hypertension or hypotension or difficulty breathing during the administration or immediately afterwards (within the following 2 hours). The patients will be treated according to I-O AE Algorithms from Appendices B and C; Investigator Brochures for Nivolumab (BMS-936558) and Relatlimab (BMS-986016). Generally, Grade 1 infusion reactions will be observed. Grade 2 or 3 infusion reactions will prompt interruption of the patient's infusion until the observed symptom returns to the level of a Grade 1 reaction. Patients will be given 25mg of Benadryl IV and 650 mg of Tylenol PO for any grade 2 or 3 reaction. The Benadryl can be repeated once for symptom resolution until the reaction returns to a level of Grade 1. If a patient has a Grade 2 or 3 reaction, subsequent infusions will be preceded by 25mg of Benadryl IV and 650mg of Tylenol PO 30 minutes prior to dosing. Grade 4 reactions will cause discontinuation of the therapy. Patients will be instructed to inform the clinical team of any symptoms including, but not limited to, fever, chills, itching, shortness of breath, stomach discomfort, diarrhea, new neurological symptoms, seizures, changes in urinary function, chest pain, palpitations, rashes or any other significant concern in between drug doses.

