4.5.19 Follow-up (Research)

Upon discharge from the hospital, a summary letter will be sent to the patient's physician of record, describing the care rendered. Dosing of study medications will commence on Day 17 (+/- 2 days). Safety monitoring for infusions is discussed in section 8.2, below. Additionally, all patients will be seen in the Outpatient Neuroscience Clinic 2 weeks (+/- 1 week) after their surgery. This visit requirement is separate from the Day 17 (+/- 2 days) study visit. If appropriate, this post-operative care visit will be conducted in the day hospital, during the Day 17 (+/- 2 days) study visit. It may also occur on 7SW, if the patient remains admitted in the hospital, post-operatively. The patients will continue to receive Nivolumab, as above, at a dose of 240mg IV every two weeks and BMS-986016 antibody at a dose of 80mg IV every two weeks until progression. The first dose of both study medications will begin on study Day 17 (+/- 2 days). Details of the infusion can be found in section 1.6.4. Between study visits, no specific precautions are needed. Patients will be reminded to call us with any clinical concerns regarding potential adverse events, including, but not limited to GI concerns, neurological compromise, signs of adrenal

insufficiency, skin lesions, hypophisitis, respiratory concerns, cardiovascular compromise, renal insufficiency or liver failure. Detailed safety monitoring procedures are outlined in section 8, below. Section 8.6 contains the list of toxicities which will prompt automatic discontinuation of the study drugs. Additionally, we will follow the I-O treatment algorithm for Nivolumab in Appendix B, below. Steroids will be used for symptomatic management as needed, per the discretion of the treating physician. Steroid use will not be a criterion for removal from the study.

Prior to documenting removal from protocol therapy, effort must be made to have all subjects complete a safety visit approximately 30 days following the last dose of study therapy.

In the absence of treatment delays due to adverse event(s), treatment may continue as specified in the above treatment modality sections or until one of the following criteria from section 8.6, below, occurs.

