8.1.1 Study Monitoring Phase 1 – Before surgical resection

Once the patient has been enrolled into the trial, they will be considered to be in Phase 1 of the trial which precedes the surgical resection of the tumor. This period will include the research surgical procedure, the monitoring period in the intensive care unit and inpatient unit and the first dose of Nivolumab. All patients will be monitored for adverse events graded as per the National Cancer Institute Common Terminology Criteria for Adverse Events.

Of note, there is a possibility, though remote, that a frozen section could indicate recurrent tumor, but that the final pathology may only demonstrate treatment effects with no viable tumor. If that is the case, the patient's microdialysis catheters and lumbar drain can be removed in the inpatient unit without returning to the operating room. The patient would then be withdrawn from the study as per 8.6, below, and would be replaced. Microdialysis catheter removal in the inpatient unit has been performed in the setting of research studies quite commonly. The microdialysis catheters in a recently completed study of regadenoson as a blood-brain barrier opening agent in glioblastoma at the NIH were removed in the intensive care unit with no morbidity.

Additionally, as noted in 8.6, below, a patient who experiences a grade 3 or 4 toxicity during Phase 1 of the trial which precludes the completion of the inpatient monitoring period will be withdrawn from the trial. At that time, the patient's microdialysis catheters and lumbar drain would be removed in the inpatient unit. Surgical resection would proceed as per standard of care if still clinically indicated. Otherwise, further standard of care treatment will be offered. The patient can also return to the care of their physicians outside of the NIH.

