In addition to our standard post-operative care for our patients, we will be specifically assessing our patients for the following adverse events that are likely to be related to the research surgical procedure – intracerebral hemorrhage, meningitis and wound infection. Any grade of adverse events, as defined by CTCAE version 5.0, which occur within the first 3 patients will trigger an evaluation by the Safety Monitoring Committee to approve the enrollment of the next patient. Any adverse event Grade 2 or higher or any delay in planned surgery in any patient at any point during the pilot trial due to an adverse event related to the experimental procedures in Phase 1 will also trigger an evaluation by the Safety Monitoring Committee (for patients enrolled at NIH) and the Data and Safety Monitoring Board (for patients enrolled at the Emory Site) to approve the enrollment of the next patient.

Infusion reaction: Monitoring for an infusion reaction will begin on day 3 of the protocol within the patient's inpatient stay. This monitoring will consist of clinical observation, with q15 minute vital signs, during the infusion and for the first two hours after infusion. Specifically, we will be checking the patients for fever, chills, shaking, itching, rash, hypertension or hypotension or difficulty breathing during the administration of Nivolumab or immediately afterwards (within the subsequent 2 hours).

For infusion reactions, the patients will be treated according to I-O AE Algorithms from Appendices B and C; Investigator Brochures for Nivolumab (BMS-936558) and Relatlimab (BMS-986016). Generally, Grade 1 infusion reactions will be observed. Grade 2 or 3 infusion reactions will prompt interruption of the patient's infusion until the observed symptom returns to the level of a Grade 1 reaction. Patients will be given 25mg of Benadryl IV and 650 mg of Tylenol PO for any grade 2 or 3 infusion reaction. The Benadryl can be repeated once for symptom resolution until the reaction returns to a level of Grade 1. If a patient has a Grade 2 or 3 reaction, subsequent infusions will be preceded by 25mg of Benadryl IV and 650mg of Tylenol PO 30 minutes prior to dosing. Grade 4 reactions will cause discontinuation of the therapy.

Additionally, the following safety monitoring procedures will be undertaken during Phase 1 of the trial:

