Monitoring for an infusion reaction and cytokine release on Day 17 (+/- 2 days) of the protocol will consist of clinical observation in the day hospital ward or 7SW (if the patient remains admitted to the hospital) of the NIH Clinical Center. The total infusion monitoring time will be expected to last 4-5 hours for most patients. First, the patient will receive Nivolumab as an IV infusion over 30 minutes. Patients with a prior Grade 2 or 3 infusion reaction will have pretreatment with 25mg of Benadryl IV together with 650mg of Tylenol PO. During both infusions, patients will have q15 minute vital signs, including temperature, pulse, blood pressure and pulse oximetry. BMS-986016 infusion will begin 15-30 minutes after completion of the Nivolumab infusion. BMS-986016 will then be given as an IV infusion over 60 minutes with ongoing monitoring. The patients will also be monitored for two hours after completion of the BMS-986016 in the day hospital or 7SW. Specifically, we will be checking the patients for fever, chills, shakes, itching, rash, hypertension or hypotension or difficulty breathing during the administration or immediately afterwards (within the following 2 hours). The patients will be treated according to I-O AE Algorithms from Appendices B and C; Investigator Brochures for Nivolumab (BMS-936558) and Relatlimab (BMS-986016). Generally, Grade 1 infusion reactions will be observed. Grade 2 or 3 infusion reactions will prompt interruption of the patient's infusion until the observed symptom returns to the level of a Grade 1 reaction. Patients will be given 25mg of Benadryl IV and 650 mg of Tylenol PO for any grade 2 or 3 reaction. The Benadryl can be repeated once for symptom resolution until the reaction returns to a level of Grade 1. If a patient has a Grade 2 or 3 reaction, subsequent infusions will be preceded by 25mg of Benadryl IV and 650mg of Tylenol PO 30 minutes prior to dosing. Grade 4 reactions will cause discontinuation of the therapy. Patients will be instructed to inform the clinical team of any symptoms including, but not limited to, fever, chills, itching, shortness of breath, stomach discomfort, diarrhea, new neurological symptoms, seizures, changes in urinary function, chest pain, palpitations, rashes or any other significant concern in between drug doses.

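### For a Grade 3 infusion reaction the protocol states two incompatible rules: premedicated re-dosing in sections 1.5.4, 1.6.7, 8.1.1 and 8.1.2, and a mandatory stop of both drugs in section 8.6, item 3(h)

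*Combined protocol and SAP*

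**What the plan says.** The infusion-reaction instructions appear in five places.

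- Section 1.5.4, for the Day 3 nivolumab dose: "If a patient has a Grade 2 or 3 reaction, subsequent infusions will be preceded by 25mg of Benadryl IV".
- Section 1.6.7, for the Day 17 combination: "Patients with a prior Grade 2 or 3 infusion reaction will have pretreatment". The dose then goes ahead.
- Section 8.1.1, for Phase 1, says of Grade 2 or 3 reactions that "subsequent infusions will be preceded by 25mg of Benadryl IV and 650mg of Tylenol PO 30 minutes prior to dosing". It sets the stop one grade higher: "Grade 4 reactions will cause discontinuation of the therapy". It also defers to the brochures: "For infusion reactions, the patients will be treated according to I-O AE Algorithms from Appendices B and C".
- Section 8.1.2, for Phase 2, repeats the 1.6.7 text, including the pretreatment of patients with an earlier Grade 2 or 3 reaction.
- Section 8.6, item 3(h), under the reasons for which subjects must discontinue: "Infusion reactions: Grade 3 or 4 infusion reactions will prompt automatic discontinuation of study drugs". The lead-in to item 3 applies the listed toxicities to nivolumab and BMS-986016 together.

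Two sections point to 8.6. Section 4.5.19 states: "Section 8.6 contains the list of toxicities which will prompt automatic discontinuation of the study drugs". Section 7.16 does the same, and mentions re-entry to nivolumab only for successfully treated Grade 1-2 events.

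**The concern.** A nurse or physician at the infusion chair will use the monitoring paragraph. For a Grade 3 reaction it tells them to pause, treat, wait for Grade 1 and give later doses with premedication. Section 8.6 says the same patient must stop both drugs and move to survival follow-up. Following the first text re-exposes someone whom the second text protects.

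The choice also touches the primary outcomes. The Day 3 infusion is the only dose before the interferon gamma readout on the fifth day after treatment (sections 9.1 and 10.2). If it is stopped, the readout may follow a partial dose. A patient discontinued on Day 3 never receives BMS-986016, so the rule decides who is exposed for the combination-safety outcome. In a study of 10 completed patients, one patient is 1/10, or 10 percentage points, of the interferon gamma proportion.

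**Working it through.** The conflict itself involves no calculation, so the two rules are set side by side by grade.

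| Grade | Sections 1.5.4, 1.6.7, 8.1.1, 8.1.2 | Section 8.6, item 3(h) | Compatible? |
|---|---|---|---|
| 1 | Observe | No stop | Yes |
| 2 | Interrupt until Grade 1, treat, premedicate later infusions | No stop | Yes |
| 3 | Same as Grade 2 | Stop both drugs | **No** |
| 4 | Discontinue | Stop both drugs | Yes |

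**Can the text be reconciled?** Four routes were tried.

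1. Section 8.1.1 does refer to 8.6: "Additionally, as noted in 8.6, below, a patient who experiences a grade 3 or 4 toxicity during Phase 1 of the trial". That sentence, like 8.6 item 2, covers only toxicity that prevents completion of inpatient monitoring. It does not narrow item 3(h).
2. The brochure algorithms are not reproduced in the documents. Whatever they say, the four paragraphs still state their own Grade 3 rule, so the algorithms could show which text to correct but could not make both texts true.
3. The qualifier at the start of the Grade 1 sentence creates no exception for Grade 3.
4. The cross-references in 4.5.19 and 7.16 make 8.6(h) the probable intention. Neither states that it overrides the infusion paragraphs.

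**Could monitoring catch a case before re-dosing?** Take a Grade 3 reaction on Day 3, and assume the investigator learns of it that day.

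- Next dose: Day 17 ± 2, that is Day 15 to 19.
- Weekly written reports to the independent medical monitor run from Week 0 through Week 2 of the inpatient stay (section 14.2), so one can precede the dose.
- Report of a possibly related Grade 3 or higher event (section 14.2): due by 3 + 7 = Day 10, which is 15 − 10 = 5 to 19 − 10 = 9 days before the dose.
- Committee evaluation after a Grade 2 or higher Phase 1 event related to the experimental procedures (sections 8.1.1 and 14.3): due within two weeks, 3 + 14 = Day 17, inside the dosing window. It is framed as approval of the next enrollment, not of re-dosing the affected patient.
- Scheduled participant-specific review point: Day 24 ± 2, that is Day 22 to 26, which is 22 − 19 = 3 to 26 − 15 = 11 days after the dose.

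Several routes can therefore act before Day 15. None says which rule applies. None can act on the immediate decision, because interrupting until Grade 1 implies that the same infusion may restart, and on Day 17 BMS-986016 follows nivolumab by 15 to 30 minutes.

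**How often?** The documents give no Grade 3 infusion-reaction rate. The nearest figure is in Appendix D: serious infusion-related reactions in 4 of 1578 patients, 4/1578 = 0.25%. As a proxy, with independent patients, the chance of at least one is 1 − (1 − 4/1578)^n:

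- n = 10 (target): about 2.5%.
- n = 25 (accrual ceiling): about 6.1%.

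Serious is not the same as Grade 3, and the 1578 include monotherapy, so these figures indicate order of magnitude only. Section 1.5.5 calls such reactions uncommon with nivolumab. Section 7.17.1.2.3 describes 72 low-grade (Grade 1 to 2) reactions in the relatlimab program. Section 7.17.1 does record one Grade 3 allergic reaction on relatlimab monotherapy at 800 mg.

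**The case against.** The best defence is that the intended rule is fairly clear. Section 8.6 is mandatory in wording and is named twice as the list of automatic stops. The conflicting text is one stock paragraph repeated, not four independent decisions. The event is rare, and several layers of oversight would see it. Much of this stands: it makes the problem narrow and easy to correct. It does not remove the problem, because the paragraphs that staff use during infusions carry the other rule, and the Day 17 text in 1.6.7 and 8.1.2 plans for patients whom 8.6 would already have stopped.

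A reader might infer three stronger things that the documents do not support.

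- That only expedited reporting could act before re-dosing. The routine weekly reports and the Phase 1 committee trigger can also fall before or within the dosing window.
- That the two sites would reach different answers because concerns go to different committees (section 4.5.20). Section 14.2 also sends possibly related Grade 3 or higher events to the DSMB without a site limit, and sends participant-specific reports to both bodies.
- That the matter is purely clinical and leaves the interferon gamma analysis untouched. A stopped Day 3 infusion can leave a partial dose before that readout.

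Section 16.2 provides for a local physician to oversee infusions when travel is precluded. That physician receives the whole protocol, including 8.6, and works under the principal investigator, so this contingency adds little.

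**Conclusion.** The inconsistency is real, confined to Grade 3, and should be fixed. Staff who follow the infusion paragraphs would re-dose a patient whom section 8.6 says must stop. Section 8.6(h) is probably the intended rule. That is an inference from the cross-references and from the re-entry wording in 7.16; no text states precedence, and the brochure algorithms could not be consulted. The chance that the conflict is tested in this trial is small, a few percent if the serious-reaction proxy is roughly right. The case for correcting it rests on patient safety and the low cost of the change, not on frequency. The power calculation is not affected. What is affected is how one patient's partial dose and missing combination exposure would be handled, and the plan does not address that.

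**What to change.** After checking the brochure algorithms, amend the paragraph in sections 1.5.4, 1.6.7, 8.1.1 and 8.1.2 to read:

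*Grade 2: interrupt until Grade 1, treat, and premedicate later infusions. Grade 3 or 4: stop the infusion, treat, and permanently discontinue both drugs per 8.6(h).*

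In the Day 17 sentences of 1.6.7 and 8.1.2, limit pretreatment to patients with a prior Grade 2 reaction. If the sponsor does intend rechallenge after Grade 3, leave those paragraphs, amend 8.6(h), and state the conditions.

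Also add three statements:

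- A patient stopped on Day 3 completes microdialysis sampling and resection if it is safe to do so.
- How a partial first dose is handled in the interferon gamma analysis. Section 3.1 replaces only those who do not complete the monitoring and resection, so this patient would otherwise count without comment.
- Such a patient never receives BMS-986016 and is not counted as exposed in the combination-safety outcome.

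The cost is a wording amendment, with no change to sample size or visits. The small downside is that a Grade 3 reactor on Day 3 may contribute only a partial dose to the interferon gamma readout and no combination-safety data.
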